9.3 Variables

The sections below describe the theoretical aspects of relevant variables. Data sources and operational definitions are discussed in [Section 9.4](#).

9.3.1 Exposure of Interest

This pregnancy registry is strictly observational and confirmed exposure to a meningococcal B vaccine within 30 days prior to LMP or at any time during pregnancy is a condition of enrollment. The exposure of interest is exposure to at least 1 dose of the BEXSERO vaccine. In the event that it cannot be ascertained to which meningococcal B vaccine the woman was exposed, an unknown exposure cohort will be established and analyzed separately.

BEXSERO is not contraindicated during pregnancy, but should be used during pregnancy only if clearly needed. Inadvertent exposure within 30 days prior to LMP or early in the first trimester (before pregnancy status is known) may be expected to occur because the age group targeted for the vaccine includes young women of reproductive potential. Data to be collected include the date of vaccination, facility (e.g., HCP office, clinic, or commercial facility such as a pharmacy or other retail outlet), dose, and lot number if available. In the event that it cannot be ascertained to which meningococcal B vaccine the woman was exposed, an unknown exposure cohort will be established and analyzed separately.

9.3.2 Outcome(s) of Interest

Major Congenital Malformation (MCM): The registry defines, classifies, and codes MCMs with criteria specified by CDC MACDP ([CDC, 2007](#)). Newborn and infant conditions that are not necessarily considered MCMs appear in the Exclusion List for the MACDP. These conditions may be included under certain circumstances by CDC criteria and will be considered “conditional defects” in the registry (e.g., skin tags, webbed toes, etc.). Please see the following link for a listing of all MACDP MCMs and conditions on the Exclusion List:

<http://www.cdc.gov/ncbddd/birthdefects/documents/macdpcode0807.pdf>.

The registry defines an MCM as any major structural or chromosomal defect or combination of 2 or more conditional defects in live-born infants, stillbirths, or fetal losses of any gestational age (including outcomes prior to 20 weeks' gestation or birth weight <500 g). This definition is consistent with, but not restricted to, the CDC MACDP definition. Clusters of conditional abnormalities (as defined by CDC MACDP) and data from aborted fetuses of less than 20 weeks' gestation, when available, will be included to increase sensitivity of monitoring. The MACDP includes conditional defects only if in the presence of a major defect. This registry will consider reports of 2 or more conditional defects as a defect case, to increase signal sensitivity and to capture instances where a combination of conditional events might constitute a major defect or syndrome.

The registry conforms to the CDC MACDP guidelines in disqualifying as defects those findings that are present in infants born at less than 36 weeks of gestation, and are attributable to prematurity itself, such as patent ductus arteriosus, patent foramen ovale, or inguinal hernias. The CDC MACDP classification does include chromosomal defects. Though vaccine exposure is not likely to contribute to a risk for chromosomal defects, the registry includes these defects to maintain this consistency with the CDC MACDP.

Live-born infants with only transient or infectious conditions or with biochemical abnormalities will be classified as being without reported MCMs unless there is a possibility that the condition reflects an unrecognized MCM. Detected and reported transient or infectious conditions or biochemical abnormalities in infants without reported MCMs and defects that are excluded by the CDC guidelines will be noted in an appendix in the registry reports.

Preterm birth: An infant born at gestational age <37 weeks

Low Birth Weight: An infant whose birth weight is <2500 g

9.3.3 Other Variables

Maternal characteristics: Age, ethnicity, race

Prenatal data: LMP, estimated date of delivery (EDD), corrected estimated date of delivery (CEDD)

Prenatal tests: Name of test, date of test, result

Obstetrical history: Previous pregnancies, live births, stillbirths, SABs, induced abortions (IABs), births with congenital malformations, family history of congenital malformations

Concurrent medical conditions

Concomitant medications and vaccines

Alcohol, tobacco, and illicit drug use

Pregnancy outcomes

Each pregnancy outcome will be classified in 1 of the following mutually exclusive categories:

- Live birth: an infant born alive
- Stillbirth: a fetal death occurring at 20 weeks' gestation or greater, or if gestational age is unknown, a fetus weighing 500 g or more
- Spontaneous abortion (SAB): fetal death or expulsion of products of conception prior to 20 weeks' gestation, or if gestational age is unknown, weighing less than 500g
 - Terminology may include missed abortion, incomplete abortion, and inevitable abortion.
- Induced Abortion (IAB): voluntary interruption of pregnancy, including pregnancy termination that occurs electively, to preserve maternal health, or due to fetal abnormalities
- Ectopic pregnancy: implantation of a conception outside of the uterus
- Molar pregnancy: a conception that results in a gestational trophoblastic tumor

Infant outcomes: Gestational age, birth weight, sex

9.4 Data Sources

The pregnant woman and appropriate members of her health care team will serve as data reporters to the registry. The registry is strictly observational; the schedule of office visits and all treatment regimens will be determined by the treating HCP. There will be no additional laboratory tests or assessments required as part of this registry. Only data noted as part of routine care will be collected. Data related to maternal characteristics will be provided by the pregnant woman or by her HCP ([Section 9.4.3](#)). Interim follow-up and outcome data will be provided by the obstetric HCP and/or pediatrician attending the birth, where accessible ([Section 9.4 – Attempts to Obtain the Follow-up Information](#)). Additionally, the teratologist/geneticist on the SAC will provide an opinion regarding the possible temporal association of the BEXSERO exposure to the development of observed defects. If additional information is needed to aid in classification or temporality assessment, the teratologist will request additional information using the targeted follow-up process outlined in [Section 9.4.2](#). The SAC will meet periodically to review the data, discuss the MCM cases and their classification and temporality with the teratologist, and reach a consensus on the coding and classification of MCMs and other primary endpoints.

HCPs may also report de-identified data to the registry. The following table provides a summary of data that will be collected at specific time points and the source of data. See Figure 9.2.3-1 for the various enrollment and data collection options used by the registry.

Table 9.4-1 Summary table of evaluations

Information requested	Registration provided by participant and/or Ob HCP	Interim prenatal follow-up (end of 2 nd trimester) provided by Ob HCP	Pregnancy outcome provided by Ob HCP and/or pediatrician attending birth	Targeted follow-up to collect information not previously obtained ^b , provided by the Ob HCP and/or pediatrician attending birth
Maternal contact information, alternate contact information, HCP contact information	X	X ^a	X ^a	
Maternal characteristics (age, ethnicity, race, etc.)	X	X ^a		
Maternal prenatal information (LMP, EDD, CEDD, prenatal test results and timing)	X	X ^a	X ^a	
Obstetrical history	X	X ^a		X
Family history of MCMs	X	X ^a		X
BEXSERO exposure information	X	X ^a	X ^a	
Concurrent conditions, concomitant medications, alcohol & tobacco use during pregnancy	X	X ^a	X ^a	
Pregnancy status		X	X ^a	
Outcome information (live birth, still birth, SAB, gestational age, birth weight, infant/fetus sex)			X	
MCM noted and description			X	
Contributing factors			X	X

Abbreviations: CEDD = corrected estimated date of deliver; EDD = estimated date of delivery; HCP = health care provider; LMP = last menstrual period; MCM(s) = major congenital malformation(s); Ob = obstetric; SAB = spontaneous abortion.

^a Obtain updated information since the previous contact.

^b Targeted follow up is designed to collect addition information (if necessary) to facilitate characterization of the fetal loss and/or MCMs.

Registration Process

Registry enrollment may be initiated by pregnant women or by their HCPs, who will act as data reporters to the registry. HCPs may also submit de-identified data to the registry. See [Figure 9.2.3-1](#) for the various enrollment and data collection options used by the registry. After applicable subject informed consent is obtained from eligible women, the reporter will be asked to complete the **Registration Form** and submit it to the registry. HCPs may also report de-identified pregnancy and outcome data to the registry. The registry will provide a variety of convenient means for reporters to communicate with and submit data to the registry.

Information Collected at Registration

Reporter Information

- Contact information for the patient (if the patient self-enrolls), as well as alternate contact information, such as a permanent address and/or next of kin.
- HCP reporter contact information

Maternal Information

- Maternal demographics (age, ethnicity, race)
- LMP
- EDD determined from LMP
- CEDD (e.g., by ultrasound), if available
- Prenatal tests (diagnostic or screening) performed, date of test, and findings including the identification of congenital anomalies

Maternal Obstetrical History

- Number of previous pregnancies
- Outcome of previous pregnancies: live births, stillbirths, SABs, IABs, ectopic pregnancies, molar pregnancies
- History of offspring with congenital anomalies
- Maternal and paternal history of congenital anomalies

Maternal BEXSERO Exposure (may be provided initially by the pregnant woman at registry enrollment and confirmed by the vaccinating HCP)

- BEXSERO administration, including dose, timing, and lot number
- *Other Conditions and Exposures*

- Concurrent maternal conditions
- Concomitant medications or vaccinations during pregnancy
- Tobacco, alcohol, and illicit drug use during pregnancy

Pregnancy Follow-up

Around the end of the second trimester and in the month of the EDD, the ***Interim Pregnancy Follow-up Form*** and ***Pregnancy Outcome Form***, respectively, will be requested from the obstetric HCP.

Information Collected at Interim Pregnancy Follow-up and Pregnancy Outcome

Interim Pregnancy Follow-up at End of Second Trimester

Pregnancy Status

- Updates to EDD (i.e., CEDD)
- Subsequent prenatal tests (diagnostic or screening) performed and findings including the identification of congenital anomalies
- Pregnancy complications (preterm labor, eclampsia, placental abruption)
- Details of pregnancy outcome if pregnancy is not ongoing as described below

Other Exposures

- Concomitant medications and vaccinations
- Tobacco, alcohol, and illicit drug use during pregnancy

Additional Information Collected at Pregnancy Outcome

Fetal Outcome

- Pregnancy outcome (live birth, stillbirth, SAB, IAB, ectopic pregnancy, molar pregnancy)
- Date of outcome of pregnancy
- Gestational age at outcome
- Fetal/infant characteristics: sex, birth weight
 - MCM(s) and assessment of potential contributing factors
 - For a fetal loss (SAB, stillbirth), factors that may have had an impact on the fetal loss and attribution

Targeted Follow-up Process

If there is an MCM or other event of interest noted, in order to properly characterize the event, additional information may be requested from the reporting HCP on the **Targeted Follow-up Form**:

- Details of the MCM/condition
- Etiology
- Outcome attribution
- Specific questions requested by GSK and/or the MCM evaluator

Attempts to Obtain the Follow-up Information

In the month that the follow-up is due, the HCP will be contacted and asked to provide follow-up information. Three subsequent attempts, as necessary, will be made every 2 weeks via various modes of communication. If there is still no response from the provider, a final communication will be sent indicating the case is lost to follow-up. If this communication prompts a response from the HCP or the requested data is later received, the case will be re-opened and assessed for evaluability. If, at any point in the follow-up process, the reporter indicates that the patient is lost to follow-up, no further attempts will be made.

Follow-up Process for Clarification of Information

For critical data points, if there are outstanding questions, discrepancies between forms, or missing data, the appropriate reporter will be contacted for clarification. Three subsequent attempts, as necessary, will be made every 2 weeks. If no further information is obtained on an otherwise evaluable case, the discrepant information in the data fields may be left blank, identified as “unspecified.” On a case-by-case basis, qualified registry staff or the principal investigator may make a determination on discrepant information (e.g., determination of partially illegible word or illogical year).

9.4.1 Operational Exposure Definition

At least 1 dose of BEXSERO administered 30 days prior to LMP or at any time during pregnancy (from conception until pregnancy outcome) will constitute exposure. In the event that it cannot be ascertained to which meningococcal B vaccine the woman was exposed, an unknown exposure cohort will be established and analyzed separately. The 30-day window prior to conception corresponds with the time to immunologic response as indicated in the BEXSERO product label ([Bexsero[®] prescribing information, 2015](#)). BEXSERO exposure will be further categorized by earliest trimester of exposure. BEXSERO is not contraindicated in pregnancy, but should be used during pregnancy only if clearly needed ([Bexsero[®] prescribing information, 2015](#)). Inadvertent exposure within 30 days prior to LMP or early in the first trimester (before pregnancy status is

known) may also be expected to occur because the age group targeted for the vaccine includes young women of reproductive potential. For this registry, gestational weeks will be estimated from the most reliable EDD as reported by the HCP. If a CEDD is provided by the HCP, it will be used instead. The date of conception will be calculated as the most reliable EDD minus 38 weeks. If the EDD is not available or never estimated, the first day of the LMP may be used to estimate gestational age. The second trimester will be considered to begin at week 14 after the date of conception or LMP, and the third trimester, at week 28. If there is a discrepancy between gestational age calculated from LMP and reported gestational age, the HCP will be asked to verify the data.

When a pregnant woman enrolls in the registry, she will be asked when and where she was immunized with the BEXSERO vaccine, or any meningococcal B vaccine if the brand is unknown. She will then be asked to provide a medical release that allows the registry to confirm with the appropriate source the exposure to a meningococcal B vaccine occurred. The registry will contact the vaccine provider to confirm the vaccination date, brand, and lot number. If HCPs provide de-identified data to the registry, they must be able to verify the vaccination with BEXSERO and date of vaccination. In the event that it cannot be ascertained to which meningococcal B vaccine the woman was exposed, an unknown exposure cohort will be established and analyzed separately.

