9.2.3 Study Population Selection

The minimum criteria required for enrollment into the registry are as follows:

- Sufficient evidence to confirm that exposure to a serogroup B meningococcal vaccine (confirmed or possible BEXSERO vaccination) occurred within 30 days prior to LMP or at any time during pregnancy

- Sufficient information to determine whether the pregnancy is prospectively or retrospectively registered (i.e., whether the outcome of pregnancy was known at the time of first contact with the registry)
- Date the pregnancy exposure is registered
- Full reporter (i.e., HCP) contact information to allow for follow-up (name, address, etc.)

In the event that it cannot be ascertained to which meningococcal B vaccine the woman was exposed, an unknown exposure cohort will be established and analyzed separately.

Enrollment in the Registry

[figure not shown]
Enrollment and data collection will be coordinated through a registry coordination center (RCC) staffed by trained registry coordinators located in the US. These registry coordinators will be the first line of communication with participants and their HCPs. The coordinators are experienced in working directly with both patients and HCPs to establish a rapport with them and assist them in fulfilling registry requirements. The team will be formally trained in the appropriate methods for handling registry calls with scripts and decision trees in place. Please also refer to [Section 10.3](#) for additional details of the RCC.

Eligible pregnant women may be enrolled in various ways. They may self-enroll in the registry by calling the pregnancy registry telephone number directly or their HCP can, with their consent, enroll them on their behalf. Alternatively HCPs may report de-identified data on pregnancy exposures and outcomes occurring within their network/health maintenance organization (HMO).

[Figure 9.2.3-1](#) outlines the process flow for enrolling registry participants under the 3 models:

1. Self-enrollment with signed informed consent or verbal consent (waiver of documentation of informed consent)
2. HCP enrollment with signed informed consent or verbal consent (waiver of documentation of informed consent)
3. De-identified data provided by HCPs under the waiver of informed consent provision.

Figure 9.2.3-1 Registry enrollment, informed consent and data collection process

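### Section 9.4.1 mixes LMP and conception as time origins: read literally, doses between the two dates are not exposure, and the trimester weeks have no single starting point

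*Combined protocol and SAP*

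**What the plan says.** **Exposure.** Protocol Section 9.4.1, the operational definition, counts as exposure "At least 1 dose of BEXSERO administered 30 days prior to LMP or at any time during pregnancy (from conception until pregnancy outcome"). The same section states: "The date of conception will be calculated as the most reliable EDD minus 38 weeks". It justifies the lead-in period as follows: "The 30-day window prior to conception corresponds with the time to immunologic response".

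**Enrollment.** Section 9.2.3 requires evidence that exposure "occurred within 30 days prior to LMP or at any time during pregnancy". Section 9.3.1 says that "confirmed exposure to a meningococcal B vaccine within 30 days prior to LMP or at any time during pregnancy is a condition of enrollment". Neither section says on which day pregnancy starts.

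**Dating.** Section 9.4 collects LMP and "EDD determined from LMP" at registration, together with a corrected date (CEDD) if there is one. At interim follow-up it collects "Updates to EDD (i.e., CEDD"). Sections 9.4.1 and 9.7.3 date gestation by the most reliable EDD, replace it by a CEDD when one is given, and allow LMP when no EDD exists.

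**Trimesters.** Section 9.4.1 says: "The second trimester will be considered to begin at week 14 after the date of conception or LMP", with the third trimester at week 28. Section 9.7.3 repeats weeks 14 and 28, gives no origin in that sentence, and stratifies the malformation (MCM) data by the earliest trimester of exposure. It leaves further subgroup detail to the SAP.

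**The concern.** Section 9.4.1 is where a programmer would look to code the exposure variable, and Section 9.7 limits the primary population to participants exposed to BEXSERO. If the operative sentence is coded as it stands, a woman vaccinated after LMP and before the calculated conception date is unexposed. A woman vaccinated the day before LMP, further from conception, is exposed. Sections 9.5 and 9.7.3 expect 99% of exposures before pregnancy is recognized, and the uncovered days lie in that period.

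The trimester sentence raises a separate, smaller problem. It names two possible origins, so the same gestational stage can fall in different trimesters depending on which is used.

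Finally, doses given before LMP are eligible, and Section 9.5 includes them in its 99%. A stratification by trimester gives them no place.

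**Working it through.** The plan states no figure for this point, so the check is a day count on its own rules.

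**Inputs**
- Lead-in period: 30 days before LMP (9.2.3, 9.3.1, 9.4.1).
- Conception: EDD minus 38 weeks = EDD − 266 days (9.4.1).
- Trimester starts: weeks 14 and 28 (9.4.1, 9.7.3).
- Interval from LMP to EDD: not stated. I assume 280 days and show 273 and 287 as a range, because a CEDD can shift it.

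**Gap in the exposure window.** Set LMP = day 0 and let L be the LMP-to-EDD interval. Conception falls on day L − 266. The literal window is days −30 to −1, then day L − 266 to outcome. The days in neither part are day 0 to day L − 267, a total of L − 266.

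| L (days) | Conception | Days left out | Length |
|---|---|---|---|
| 273 | day 7 | 0 to 6 | 7 |
| 280 | day 14 | 0 to 13 | 14 |
| 287 | day 21 | 0 to 20 | 21 |

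**Against the enrollment rule.** There are two readings.
- If pregnancy in 9.2.3 and 9.3.1 is counted from LMP, enrollment covers day −30 to outcome without a break. It then accepts the 7 to 21 days that 9.4.1 leaves out.
- If the 9.4.1 parenthesis also defines pregnancy for enrollment, the sections agree with each other and eligibility has the same hole.

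**Trimester boundaries.** From LMP, week 14 is day 14 × 7 = 98 and week 28 is day 28 × 7 = 196. From conception, add L − 266 days:
- L = 280: days 112 and 210, that is LMP weeks 16 and 30.
- L = 273: LMP weeks 15 and 29.
- L = 287: LMP weeks 17 and 31.

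The shift is two weeks on the main assumption and one to three over the range. Suppose the phrase means conception when an EDD exists and LMP otherwise. Two women at the same stage would then still have boundaries about two weeks apart.

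**Late CEDD.** If a CEDD lies 287 days after the reported LMP, the implied LMP (CEDD − 280) is 7 days later than reported. A window opening 30 days before the implied LMP opens 23 days before the reported one. Doses 30 to 24 days before the reported LMP (7 days) were eligible at enrollment and would fall outside the re-dated window. Any repair therefore has to say which dating decides eligibility.

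**After the repair.** With one window from day −30 to outcome, the gap is 0 days. With weeks counted from EDD/CEDD minus 280 days, trimesters two and three start at gestational weeks 14 and 28 for every woman. The detectable effect sizes in Table 9.5-1 depend only on the number of live births and the reference prevalence, so none changes.

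**The case against.** The strongest reply is that the intent can be recovered. Later in Section 9.4.1, inadvertent exposure is placed in the 30 days leading up to LMP or the opening weeks of the first trimester, with no mention of a break. The enrollment sections also use LMP. The strict reading is selective too: the operative sentence omits the word within before its 30 days, and nobody would take that to mean a single day. This stands as evidence that the gap is unintended. It does not change what the operative sentence says.

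A reader might go further in four ways that the documents do not support.
- **That enrollment and exposure flatly contradict each other.** They do so only if pregnancy is counted from LMP, and the enrollment sections do not say so.
- **That women will be dropped.** The exclusions in Section 9.7 are invalid reports, losses to follow-up and retrospective reports. Unknown-brand exposure is analyzed separately, and unconfirmed patient reports are summarized separately. None tests the dose date against conception.
- **That there is a second operative window of 30 days before conception.** That sentence gives a rationale and misnames the anchor.
- **That the effect can be sized.** The number of doses in the uncovered days is not given. The expectation that 99% of prenatal exposures fall in the first trimester cannot strictly bound the trimester effect, because it rests on the boundary that is unclear.

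On trimesters, it is fair to say that the week-14 sentence in 9.7.3 follows the EDD/CEDD dating rule in the same paragraph, and that the SAP could settle the stratum for doses before LMP. The ambiguity in 9.4.1 remains: the hierarchy chooses the source of the date and does not say which day is week 0.

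**Conclusion.** The point holds as a defect in the written definition. Taken literally, Section 9.4.1 leaves out the days from LMP to conception: about 14 on the assumption that EDD is LMP plus 280 days, and 7 to 21 for 273 to 287. Depending on when pregnancy starts for enrollment, the result is either a mismatch between eligibility and exposure or the same hole in both. Exclusion of eligible women is a risk of coding the text as it stands and is not a planned step.

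The two-origin trimester wording needs no dating assumption to be ambiguous. Its size, about two weeks, does rest on the 280 days. It affects a descriptive MCM stratification and probably few doses. The exposure wording matters more, because it concerns the period in which most exposures are expected. It should be corrected before the exposure variable is programmed.

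**What to change.** 1. In 9.4.1, state exposure as one continuous window from 30 days before LMP through pregnancy outcome, in the same words as the enrollment rule. Delete the parenthesis that starts pregnancy at conception. In the rationale sentence, "The 30-day window prior to conception corresponds with the time to immunologic response", replace conception by LMP.
2. In 9.4.1 and 9.7.3, say that weeks 14 and 28 are gestational weeks dated by the plan's existing hierarchy: CEDD, else EDD, and LMP only if neither exists. With a CEDD or EDD, week 0 is that date minus 280 days. Remove conception as an alternative origin from the trimester sentence.
3. State that eligibility is judged on the dating available at enrollment. A later CEDD updates the trimester and does not remove an enrolled woman from the exposed population.
4. Assign doses given before LMP to a named stratum. This can be done in the SAP.

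The cost is a short protocol amendment, which under Section 10.4 needs the sponsor's agreement and IRB approval. No new data are needed: vaccination date, LMP, EDD and CEDD are already collected.
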